5.5.1.3 Ophthalmologic toxicities

All subjects should receive prophylactic administration of steroid ophthalmic solution for each administration of ABT-414. The recommended type, dose, and schedule of eye drops is as follows: dexamethasone 0.1% solution, 2 drops (GTTs) in each eye (OU) every 8 (q8) hours to start 48 hours prior to ABT-414 dosing and continue for a total of 7 days (or 21 doses total). Subjects developing ophthalmologic toxicities despite the use of prophylactic steroids must have an examination by an ophthalmologist, including a thorough slit-lamp exam, to evaluate for the presence of epithelial microcysts. If ocular toxicity is grade 1 or 2, subjects may continue on ABT-414 without dose delay, reduction or suspension, but they must receive treatment from an ophthalmologist and will need to have repeated eye examinations. For grade 3 or 4 toxicity, ABT-414 must be suspended until resolution of ocular symptoms to grade 1. Afterward, patient may re-initiate treatment at a lower dose upon discussion with the medical monitor. No dose modification below a total dose of 0.5 mg/kg is allowed. Re-treatment at a lower dose of ABT-414 has generally resulted in no reported eye event or less severe toxicities.

5.5.1.3.1 Prophylaxis

In efforts to prevent the formation of some of these microcysts, dexamethasone and other steroids may be used to slow down the turn-over of the transient amplifying cells, thereby protecting them from the damage caused by a toxin that targets cells in rapid division. Although early use has shown that steroid eye drops may help reduce the severity of symptoms by preventing the formation of microcysts, they generally do not get rid of them completely. Given that the steroid eye drops are to be used to protect the transient amplifying cells during exposure to MMAF, the best time to administer them is around the time of infusion when the levels of MMAF are at their peak. The prolonged use of steroid eye drops outside of the time when there is MMAF exposure is not recommended as they may cause other side effects and prevent the healing process.

Intra-ocular pressure (IOP) should be monitored as appropriate during ophthalmologic examination. If increase in IOP occurs, it should be controlled with IOP-lowering medication according to the investigator discretion.

5.5.1.3.2 Treatment once symptoms occur

Once corneal microcysts have formed, there are no known therapies that can remove them from the cornea. Thus, only therapies that can control symptoms and promote healing are indicated. Thus, steroid eye drops may not be the best strategy as they may inhibit the healing process. Rather, lubricating drops and gels, corneal bandages, and antibiotic drops (if an infectious process is evident) are the best strategy for the promotion of healing and control of symptoms. Frequent monitoring by an ophthalmologist is also recommended at this time to make sure that the appropriate bandaging and antibiotics are prescribed for the promotion of healing and adequate alleviation of symptoms.

5.5.1.3.3 Discussions with patients

It is important that patients understand this toxicity and the importance of following the recommendations for the eye drops as well as the rapid reporting of their symptoms. It is also important to let them know that at this time, in all of the patients, symptoms have improved over time and there is no evidence to suggest that there is any permanent damage done to the cornea. It does take some time, however, for symptoms to resolve and thus an immediate reversible of symptoms should not be promised. At least 3-4 weeks must take place for the regeneration of the cornea; this is an approximate timeline for when symptoms should improve and corneal healing should take place.

5.5.1.3.4 Ophthalmological photography

Sites that agree will be asked to provide ophthalmologic photography (e.g slit lamp, confocal microscopy, Heidelberg Retinal Tomography [HRT3] etc.) of corneal abnormalities.

Patients treated with ABT-414 and experiencing ocular side effects may be presented with an approved optional consent form asking them for the release of these photographs of their eyes. If patients agree and sign and date the form, copies of new or already taken photographs will be sent to AbbVie. Included are the trial number, patient number and the date the photograph was taken (either written on the photograph or within the file name) and the date of patient consent confirmed by the (sub)-investigator or delegate. Consent forms and photographs should be filed in patient notes and site file. No other patient identifiers should be present on the data provided to AbbVie. Photographs collected during scheduled visits should be of the eye or part of the eye only and not including the full face, nose, ear, or mouth. If two eyes are affected these should be submitted as two separate photographs.

5.5.1.4 Hepatic Laboratory Abnormalities (ABT-414)

ABT-414 Dose Modification Guidelines for Hepatic Laboratory Abnormalities:

Hepatic Laboratory Abnormality	ABT-414
ALT or AST >5x ULN* but ≤ 20x ULN (and TBL ≤ 2x ULN)	
ALT or AST > 20x ULN or ALT or AST >3x ULN and TBL >2x ULN	

* If elevated at baseline, either 5x the baseline value or 8x ULN, whichever is lower

For guidelines for pediatric patients, see [Appendix I](#).

5.5.2 Lomustine

Patients requiring more than two consecutive lomustine dose reduction (i.e. only two dose reductions are allowed based on product labeling) will discontinue lomustine treatment. Study efficacy evaluations will not be modified because of dose delays. Dose modifications are based on toxicity during the prior treatment cycle. If multiple toxicities are seen, the dose administered should be based on the dose reduction required for the most severe grade of any single toxicity.

5.5.2.1 Dose levels of lomustine

The lomustine dose will be rounded to the closest multiple available; the dosage is calculated based on BSA but a maximum dose (cap) is used. Two dose levels of lomustine will be used.

Dose	Dose mg/m ² q6 weeks
0	110 mg/m ² (cap 200 mg)
-1	90 mg/m ² (cap 160 mg)
-2	70 mg/m ² (cap 120 mg)

5.5.2.1.1 Hematological toxicity

In general, the nadirs for hematological toxicity with lomustine are expected between days 28 and 35. In case of hematological toxicity grade 3 or 4 (according to CTCAE v. 4.0), the dosage of the next cycle will be reduced with one level. If the hematological toxicity does not recover within 4 weeks or if after recovery the hematological toxicity recurs at a subsequent cycle to grade ≥ 2 , lomustine treatment should be discontinued. No more than two dose reductions are allowed.

Administration of next cycle: If blood examination on day 42 or 43 (which may have been obtained in the prior 48 hours) show recovery of platelets above 100×10^9 and granulocytes counts above 1.5×10^9 , the next dose may be administered on day 43. If this is not possible, hematologic parameters will be repeated weekly and the next cycle will be given upon recovery of granulocytes and platelets. If after 4 weeks the patient has still not recovered, they should discontinue study treatment and stay on study until progression.

5.5.2.1.2 Non hematological toxicity

- Liver toxicity grade >2 : the dose of the next cycles will be reduced by 1 dose level
- In case of pulmonary toxicity grade 1-2, or appearance of symptoms, DLCO will be performed.
 - If DLCO $\geq 60\%$ of the predicted value: patient will receive the next cycle at the same dose
 - If DLCO $< 60\%$ of the predicted value: patient should discontinue study treatment and stay on study until progression
- In case of pulmonary toxicity grade 3 or higher, patient should discontinue study treatment and stay on study until progression
- Any grade 4 non hematological toxicity: the patient should discontinue study treatment and stay on study until progression
- If the non-hematological toxicity does not recover within two weeks or if non hematological toxicity recurs at the next cycle to a grade ≥ 2 the patient should discontinue study treatment and stay on study until progression

5.5.3 Temozolomide

The following dose levels of TMZ will be used: 1000 mg/m² per cycle (5 days 200 mg/m²); 750 mg/m² per cycle (5 days 150 mg/m²); 500 mg/m² per cycle (5 days 100 mg/m²).

Dose	Dose mg/m ² q4 weeks
+1	200 mg/m ²
0	150 mg/m ²
-1	100 mg/m ²

- ◆ The starting dose in cycle 1 is 150 mg/m² temozolomide on day 1-5, to be taken at least 2 hours after a meal, on empty stomach.
- ◆ Patients with no or only grade 1 toxicities in cycle 1 are allowed to dose escalate in any subsequent cycles to 200 mg/m² day 1-5.
- ◆ In case of nadir (usually ± day 21) CTCAE hematological toxicity grade 3 or 4, the dosage of the next cycles will be reduced by one dose level.
- ◆ In case of CTCAE grade 3 non-hematological toxicity, the dosage of TMZ of the next cycles will be reduced by one dose level.
- ◆ In case of CTCAE grade 4 non-hematological toxicity, the patient should discontinue treatment.
- ◆ In case of grade 3 cardiac toxicity, the patient should discontinue treatment.
- ◆ In case of toxicity requiring dose reductions in patients treated at the 100 mg/m² daily level (500 mg/m² per cycle) the patient goes off treatment.
- ◆ In case of dose reductions, dose re-escalation is not allowed.
- ◆ In case of hepatic laboratory abnormalities, see [Appendix L](#) for guidelines on repeat testing and evaluation (regardless of the assessed relationship to study treatments).

Nadir granulocytes	Nadir thrombocytes	Temozolomide modification
≥ 1.0×10 ⁹	≥ 50×10 ⁹	Dose unchanged
< 1.0×10 ⁹	<50×10 ⁹	Decrease dose by 1 dose level

Administration of next cycle: If blood examination on day 28 or 29 (which may have been obtained in the prior 48 hours) show recovery of platelets above 100×10⁹ and granulocytes counts above 1.5×10⁹, the next dose may be administered on day 29. If this is not possible, hematologic parameters will be repeated weekly and the next cycle will be given upon recovery of granulocytes and platelets. If after 2 weeks the patient has still not recovered, they should discontinue study treatment and stay on study until progression.

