6.2 Before randomization

All pretreatment evaluations should be performed within 2 weeks before randomization.

The baseline evaluations include:

- Histologically confirmed *de novo* (primary) glioblastoma with unequivocal first progression after RT concurrent/adjuvant TMZ chemotherapy either at least 3 months after the end of radiotherapy or have tumor progression that is clearly outside the radiation field or have tumor progression unequivocally proven by surgery/biopsy
- Informed consent and consent for future studies
- Demographics (height, weight, race, ethnicity)
- Complete medical history, including documentation of any clinically significant medical condition
- Prior anti-cancer therapy (including start and end dates for prior TMZ chemotherapy and RT)
- Physical examination including, but not limited to, WHO performance status and neurological evaluation
- Ocular examination by an ophthalmologist
- Vital signs (blood pressure, pulse rate and body temperature)
- Quality of life assessment, including EORTC QLQ-C30 and EORTC-BN20 (see section [10.1](#))
- 12-lead ECG
- ◆ Concomitant medications
- ◆ Steroid intake
- Assessment of all adverse events according to CTCAE 4.0
- Hematology (WBC, absolute neutrophil count, lymphocytes, hematocrit, hemoglobin and platelet count)
- Biochemistry (serum creatinine, total bilirubin, ASAT, ALAT, alkaline phosphatase, phosphate, total protein, albumin, sodium, potassium, calcium and chloride)
- Serum or urine pregnancy test for WOCBP within 72 hours prior to randomization.
- Gadolinium-enhanced MRI of the brain within 2 weeks prior to randomization. For operated patients, the post-surgery MRI within 48 hours is mandatory and can be used as baseline. However, if a subject is not randomized within 2 weeks from the post-surgery MRI, then a new MRI scan is required and will be used as baseline.
- Demonstrated EGFR gene amplification by centralized testing using EGFR FISH developed by Abbott Molecular.
- Although not considered necessary activities prior to randomization, the following samples are optional and all subjects randomized may consent to participate in future translational research:
 - Tumor tissue remaining following EGFR amplification testing for future TR projects (optional samples, see section [11.8](#))
 - Whole blood for germline DNA and TR projects (optional samples, see section [11.8](#))

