6.3.4 Day 21 of each cycle - Arm 1 and 3B patients only

All day 21 evaluations should be performed within 3 days before or 3 days after day 21 of the cycle.

- Hematology (as 6.2 - this can be omitted once treatment at the present dose level was shown to cause only grade 1 or less hematological toxicity at day 21 and only grade 2 or less at day 28).

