8.2.3.7.1 Hematological parameters

The worst value of each hematological category will be identified and graded for each patient. Frequencies and percentages of each category will be tabulated per arm. A table with grade 3/4 frequencies and percentages will be provided.

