11.4.1 Assessment of Potentially Clinically Significant Laboratory Values

For selected laboratory variables, the number and percentage of subjects who had at least one post-baseline observation meeting the pre-defined criteria for potentially clinically significant values will be provided for each variable. If a subject did not have the laboratory measurement at baseline but had a post-baseline measurement which met the pre-defined criteria, this subject is considered as meeting the criteria for potentially clinically significant laboratory values for the measurement.

Pre-defined criteria for potentially clinically significant laboratory values are given in [Table 8](#) and [Table 9](#) below based on NCI CTCAE criteria:

Table 8. Criteria for Potentially Clinically Significant Laboratory Values – Hematology Variables

Hematology Variables	Units	Definition of Potentially Clinically Significant Values (NCI CTCAE Grade ≥ 3)
Hemoglobin	g/L	< 80
White blood cell count	$10^9/L$	< 2
Neutrophil count	$10^9/L$	< 1
Lymphocyte count	$10^9/L$	< 0.5
Platelet count	$10^9/L$	< 50

Table 9. Criteria for Potentially Clinically Significant Laboratory Values – Chemistry Variables

Chemistry Variables	Units	Definition of Potentially Clinically Significant Values (NCI CTCAE Grade ≥ 3)	
		Low	High
Total bilirubin			> $3.0 \times \text{ULN}$
Albumin	g/L	< 20	
Aspartate aminotransferase (AST/SGOT)			> $5.0 \times \text{ULN}$
Alanine aminotransferase (ALT/SGPT)			> $5.0 \times \text{ULN}$
Alkaline phosphatase			> $5.0 \times \text{ULN}$
Creatinine			> $3.0 \times \text{ULN}$
Sodium	mmol/L	< 130	> 155
Potassium	mmol/L	< 3.0	> 6.0
Total calcium	mmol/L	< 1.75	> 3.1

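### Protocol 5.5.3 gives two opposite TMZ dosing answers when grade 3/4 hematological toxicity at nadir spares granulocytes and platelets

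*Protocol*

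**What the plan says.** Protocol section 5.5.3 sets three TMZ dose levels: 200, 150 (the starting dose) and 100 mg/m2 on days 1 to 5.

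- **Bullet.** For nadir "CTCAE hematological toxicity grade 3 or 4, the dosage of the next cycles will be reduced by one dose level". No blood parameter is named or exempted.
- **Table, row 1.** Nadir granulocytes at least 1.0 x10^9 and thrombocytes at least 50 x10^9: "Dose unchanged".
- **Table, row 2.** Both counts shown below those limits: "Decrease dose by 1 dose level". No and/or appears between the two columns in the text available.
- **Permanence.** "In case of dose reductions, dose re-escalation is not allowed". A patient who needs a reduction at 100 mg/m2 goes off treatment.

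The nadir count is scheduled in protocol section 6.3.4 ("Day 21 of each cycle - Arm 1 and 3B patients only"), that is, in the two arms that receive TMZ. That section refers back to the panel in section 6.2: "Hematology (WBC, absolute neutrophil count, lymphocytes, hematocrit, hemoglobin and platelet count". SAP section 11.4.1, Table 8, gives limits for five of these parameters under the column head "Definition of Potentially Clinically Significant Values (NCI CTCAE Grade ≥ 3".

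**The concern.** The bullet's trigger is a toxicity category; the table's trigger is two specific counts. The panel drawn at nadir covers more than those two counts, and the SAP attaches grade 3 limits to three further parameters. A site holding one laboratory report can therefore reach opposite decisions according to which part of 5.5.3 it follows.

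What is at stake is consistent treatment and safety, not the arithmetic of the design. TMZ is half of the Arm 1 regimen and the whole of the Arm 3B control, and the trial is open-label. A choice of reading that differs between sites would feed into TMZ dose and discontinuation. It would then reach the SAP's summaries of dose modifications with their reasons (section 9.1) and of adverse events leading to TMZ reduction or discontinuation (section 11.2).

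**Working it through.** The plan gives no figure to reproduce here. The check sets the two rules side by side, one parameter at a time.

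**Inputs.** The bullet and table are in protocol 5.5.3 and the panel in protocol 6.2. The grade 3 or higher limits come from SAP Table 8: neutrophils < 1, platelets < 50, lymphocytes < 0.5 and WBC < 2 (all x10^9/L), and hemoglobin < 80 g/L.

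**Comparison.** In the last three rows granulocytes are at least 1.0 and platelets at least 50.

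| Nadir finding | Bullet | Table | Result |
|---|---|---|---|
| Granulocytes < 1.0 and platelets < 50 | reduce | reduce | agree |
| Only one of these two counts low | reduce | row 1 does not apply; row 2 lacks and/or | no contradiction |
| Lymphocytes < 0.5 | reduce | unchanged | conflict |
| WBC < 2 | reduce | unchanged | conflict |
| Hemoglobin < 80 g/L | reduce | unchanged | conflict |

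**Worked case.** Take lymphocytes 0.4, granulocytes 2.0, platelets 120 x10^9/L and hemoglobin 110 g/L. WBC is at least 2.0 + 0.4 = 2.4, above its limit of 2, so lymphocytes are the only grade 3 or higher value. The bullet reduces by one level. Table row 1 is met, since 2.0 ≥ 1.0 and 120 ≥ 50, so the dose stays.

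**Size for one patient.**

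- From 200 to 150 mg/m2: 150/200 = 0.75, a cut of 25%.
- From 150 to 100 mg/m2: 100/150 = 0.67, a cut of 33%.
- From 100 mg/m2: TMZ ends.

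Under the bullet, repeated isolated nadirs end TMZ at the second occurrence for a patient still on 150 mg/m2, and at the third for one who had escalated to 200. Under the table nothing changes in either case.

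**Does any other text settle it?** No section says that the table defines or limits the bullet, or that lymphopenia, leukopenia or anemia is exempt. Elsewhere in 5.5.3, where only two counts are meant, the protocol names them: the condition for starting the next cycle cites platelets and granulocytes. Protocol 8.2.3.7.1, a safety-analysis rule, treats hematological toxicity as wider than two counts: "The worst value of each hematological category will be identified and graded for each patient".

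**The case against.** The strongest reply is that the table simply spells out the bullet. Its limits match the grade 3 cut-offs for neutrophils and platelets, and the next-cycle rules for both TMZ and lomustine look only at those counts. Eligibility sets no floor for lymphocytes or WBC. SAP Table 8 and protocol 8.2.3.7.1 serve safety tabulation, not dosing. This is a sensible guess at intent, and many investigators may act on it. It does not settle the point, because the protocol nowhere says so and the bullet stands as an independent instruction.

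Several limiting points do stand:

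- A reader might infer that the two rules conflict for grade 3/4 hematological toxicity in general. They do not; for granulocytes and platelets they agree.
- A reader might call the single-low-count case a second contradiction. The bullet covers it and nothing gives the opposite answer. The table was also read from PDF, so a lost and/or cannot be excluded. It is a minor wording point.
- Isolated grade 3 anemia is less likely than the other two cases. Protocol 5.5.4.1 allows transfusion or erythropoietin to hold hemoglobin above 6.2 mmol/L, which section 3.2 equates to 9.9 g/dl, that is 99 g/L against the 80 g/L limit.
- Going off TMZ is not always going off protocol treatment. Sections 5.4 and 5.5 let an Arm 1 patient continue ABT-414. Section 5.5 also directs reductions in that arm at the likely causative agent.
- Escalation to 200 mg/m2 is open only to patients with no more than grade 1 toxicity in cycle 1, so the three-step path starts from a selected group.

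**Conclusion.** The point holds in a narrow form. For grade 3/4 toxicity confined to lymphocytes, total WBC or hemoglobin, section 5.5.3 gives two stated rules with opposite and lasting consequences.

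Its size across the trial cannot be given. A planning count of patients dosed with TMZ is available: 240/3 = 80 in Arm 1, plus 40% of 80 = 32 in Arm 3B, so 112. The 40% is the historical share relapsing later, from protocol section 1.2. That is the group to whom the rule applies, not the number affected. The documents give no frequency for isolated nadirs of this kind, so any count of affected patients would rest on an invented rate.

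A reader might also infer a threat to H1, the OS comparison of Arm 1 with Arm 3. The documents do not support that. OS is analysed by intention to treat, and nothing shows a change in alpha, power or the number of deaths required. SAP 9.1 summarises dose modifications and their reasons by arm, which would let large differences in practice be seen.

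The conclusion assumes that the bullet is read as written, with no unstated exemption, and that the SAP limits represent the CTCAE grading used for dosing.

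**What to change.** Reconcile the bullet and the table in protocol 5.5.3 so that both name the same blood parameters as the trigger for a TMZ reduction. As a minor wording point, state in the table's second row whether either or both counts must be below the limit. Which parameters apply is a decision for the clinical team and is not proposed here.

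The cost is one protocol clarification. Section 5.5.3 already serves both TMZ arms, so one edit covers Arms 1 and 3B. The sample size, testing sequence and SAP efficacy analyses are untouched.

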5.5.4 Concomitant treatments

5.5.4.1 Prophylactic treatments

Anti-emetic prophylaxis should be given to lomustine treated patients on day 1 and to TMZ treated patients on day 1-3 or day 1-5 of every treatment cycle per local practice, and thereafter as clinically necessary. The use of 5HT-3 antagonists is recommended, and it is recognized they may cause constipation.

Hematopoietic growth factors: The prophylactic use of growth factors is not permitted during the screening period as a low hematologic lab value could be masked. Patients may receive red cell transfusions or erythropoietin to maintain hemoglobin > 9.9 mg/dL or 6.2 mmol/L.

5.5.5 Other concomitant medication

Corticosteroids should be used in the smallest dose possible to control symptoms of cerebral edema and mass effect, and should be reduced and/or discontinued if possible.

No other anticancer agents or investigational drugs are allowed during the study or within 28 days before the inclusion into the trial, nor the participation into another study on investigational agents.

The use of live attenuated vaccines is prohibited during the study and for a period of 49 days after the end of ABT-414 administration.

The uses of concomitant medications that are contraindicated per the national prescribing information are prohibited during the conduct of the study

All concomitant medication will be collected on the CRFs.

6 Clinical evaluation, laboratory tests and follow-up

Patients with histologically confirmed glioblastoma may register and have their tumor tissue screened after diagnose and before tumor progression. Eligibility at the time of tumor progression will depend on the confirmation of EGFR amplification during the screening, the fulfillment of all other in- and exclusion criteria and the trial status (whether the study is still open for accrual).

Tumor tissue for EGFR assessment should be prepared and sent to central lab as described in the study specific study manual.

